6. STUDY ASSESSMENTS

Due to current status of COVID-19 pandemic, clinical research activites have been affected and are being conducted as recommended by institutional guidelines to minimize potential exposure to SARS-CoV-2 for both research subjects and clinical research study team. Study investigational product(s) may be mailed to participants as determined by PI. For international patients, they may be able to obtain over the counter vitamin D3 and/or omega 3 fish oil locally (in their country of residence) if the investigational product cannot be mailed overseas (at the discretion of the PI).

In addition, the study team will try to conduct as much as possible “remote” study visits (e.g. telephone communication, video conferencing, obtaining study test results from Quest Diagnostics Lab) to obtain required SOE information.

6.1. General Assessments

Patients visits will occur for all subjects at baseline (day 0), and every four months thereafter (month 4, 8, and 12) and consist of treatment adherence and outcome assessments. Subjects will be provided with supply of study drugs to take home and administer orally. Subjects will be educated and trained for the drug administration and study personnel will evaluate drug returns and treatment adherence. Subjects will be advised to bring the used medication back to site during their next visit. At the end of

one year, all subjects will continue with assessments up to an additional one year (months 16, 20, and 24).

The time each assessment will be performed relative to dosing is shown in the Schedule of Study Activities (Appendix 1).

General assessments include:

- Medical history: To determine if there are any clinically significant diseases or medical procedures other than the disease under study.
- Physical examination: Includes any body system with clinical signs or reported symptoms of adverse events and weight loss.
- Concomitant medications
- Adverse events

6.2. Enrollment

The research study will be explained in lay terms to each potential research participant. The potential participants will sign an informed consent before undergoing any study procedures. The consent form will be reviewed with participants and the participants will be given time to review the written consent form and ask questions. The participant will be given a copy of their signed consent form.

6.3. Screening (visit 0) and Baseline (visit 1) visits

Patients will be asked to sign consent for screening to determine eligibility. Patients will receive a physical exam, medical history will be taken, and basic physical parameters will be recorded (height, body weight, heart rate, blood pressure). Blood will be drawn for laboratory assessments (see section 6.5) for evaluation of inclusion and exclusion criteria.

A patient that meets the inclusion/exclusion entry criteria will be randomized to one of the two treatment arms. Blood will be drawn for baseline visit (visit1) assessments. The patient will receive the first treatment dose within 48 hr from the baseline visit.

6.4. Diabetes Management

During the study period, all participants will receive “intensive” management of their diabetes. The patients will continue to see their primary endocrinologist during the study period. All participants will be expected to take a sufficient number of daily insulin injections to meet the glycemic targets. In general, the expectation is that all participants will receive at least three injections of insulin daily, including short- and long-acting insulin preparations, or will utilize continuous subcutaneous insulin infusion (CSII insulin pump).

Glucose levels should be checked either via continuous glucose monitor or manually at least 4 times daily via the study participant’s glucometer. Records of glucose measurements will be kept as source documentation. Insulin use and hypoglycemia events will be recorded at each visit. Participants will be

required to record the daily amount of insulin they have used at each study visit (+/- 7 days) using the 7-day Blood Sugar and Hypoglycemia log provided. Insulin pump data or smart insulin pen data will be used for documentation of insulin use in lieu of the 7-day blood sugar log for those participants using these devices.

Upon review of these records, the investigator may make adjustments in the insulin regimen, refer a participant to a registered dietitian or if necessary take other approaches that will help to maintain or improve a participant's glucose control.

6.5. Laboratory Assessments

The following laboratory assessments will be performed during the study:

- Chemistrys (sodium, potassium, chloride, CO₂, glucose, BUN, creatinine)
- Liver function tests (ALT, AST, alkaline phosphatase, total protein, albumin, total and direct bilirubin)
- Hematology (complete blood count with differential, platelets, Prothrombin time [PT/PT-INR])
- Pregnancy test as appropriate
- Autoantibodies (IA2, GAD65, ZnT8, insulin autoantibodies are induced by insulin injections and thus are not useful at this stage)
- Samples for serology (i.e. Hepatitis B, Hepatitis C, EBV, CMV and Human Immunodeficiency Virus) and HbA1c
- 4-hours Mixed Meal Tolerance Test (MMTT)
- Samples for 25OH vitamin D levels and AA/EPA ratio

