5.4.2.2. Modification or Discontinuation of Vitamin D

Vitamin D is likely safe when taken by mouth in recommended amounts. Most people do not commonly experience side effects with vitamin D, unless too much is taken. Some side effects of excess vitamin D include weakness, fatigue, sleepiness, headache, loss of appetite, dry mouth, metallic taste, nausea, and vomiting.

Taking vitamin D for long periods of time in doses higher than 4000 units daily is possibly unsafe and may cause excessively high levels of calcium in the blood. However, much higher doses are often needed for the short-term treatment of vitamin D deficiency.

Vitamin D in very high doses can make the intestines absorb too much calcium which can cause high levels of calcium in the blood (hypercalcemia). This can cause side effects including nausea, vomiting, constipation, poor appetite, weakness, weight loss, confusion and disorientation. Hypercalcemia can also lead to kidney stones, damage to the kidneys, and cause calcium deposits in heart and lungs. We will monitor blood levels of vitamin D to minimize the risk of these side-effects.

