5.4.8. Risk to the Subjects

The risks of these over the counter drugs is summarize below:

- Omega-3 Fatty Acids may cause gastrointestinal side- effects including stomach pain or discomfort, burping, heartburn, vomiting, constipation, diarrhea, nausea, and change in the sense of taste. Joint pain may be a side effect as well.
- Vitamin D in very high doses can make the intestines absorb too much calcium which can cause high levels of calcium in the blood (hypercalcemia). This can cause side effects including nausea, vomiting, constipation, poor appetite, weakness, weight loss, confusion and disorientation. Hypercalcemia can also lead to kidney stones, damage to the kidneys, and cause calcium deposits in heart and lungs. We will monitor blood levels to minimize these risks.

Allergic reaction: As with any drug, it is possible that subjects could experience an allergic reaction to OMEGA-3, or Vitamin D. Such allergic reactions include: itching, skin rash, sudden drop in blood pressure, loss of consciousness and/or associated with seizures, including the possibility of death.

Blood draw risks: Drawing blood may cause temporary pain from the needle stick, bruising or swelling at the site, and rarely, infection or fainting.

Hypoglycemia: These medications could lower blood sugar too much (hypoglycemia). This could make subjects feel tired, dizzy, sweaty, and/or nauseated. Also, it could cause heart to feel as if it is racing. There may also be other effects. Untreated hypoglycemia could cause convulsions, loss of consciousness, and can lead to death. The clinical research team will provide added training and education to subjects to better manage hypoglycemia and other diabetes related complications.

Unknown Risks: The experimental drug may have side effects that no one knows about yet. The researchers will let you know if they learn anything that might make you change your mind about participating in the study.

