7.1.7. Recording Adverse Events

To improve the quality and precision of AE data, **Investigators should observe the following guidelines:**

- Whenever possible, use recognized medical terms when recording AEs on the AE page of the CRF. Do not use colloquialisms, jargon, or abbreviations.
- If known, record the diagnosis (ie, disease or syndrome) rather than component signs and symptoms on ae pages of the CRF (eg, record “congestive heart failure” rather than “dyspnea”, “rales”, and “cyanosis”). However, signs and symptoms that are considered unrelated to an encountered syndrome or disease should be recorded as individual AEs on the CRF page. For example, if congestive heart failure and severe headache are observed at the same time, each event should be recorded as an individual AE.
- Adverse events occurring secondary to other events (ie, sequelae) should be identified by the primary cause. A primary ae, if clearly identifiable, generally represents the most accurate clinical term to record on ae pages of the CFR. If a primary SAE is recorded on an AE CRF page, events occurring secondary to the primary event should be described in the narrative description of the event.
- Laboratory abnormalities that are defined as clinically significant are to be considered AEs and recorded on the AE CRF page.

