7.1.10. Laboratory Test Result Abnormalities

The following laboratory test result abnormalities should be captured on the non-serious AE CRF page or SAE Report Form (paper or electronic) as appropriate:

- Any laboratory test result that is clinically significant or meets the definition of an SAE
- Any laboratory test result abnormality that required the subject to have study drug discontinued or interrupted
- Any laboratory test result abnormality that required the subject to receive specific corrective therapy.

It is expected that wherever possible, the clinical rather than laboratory term would be used by the reporting investigator (e.g. anemia versus low hemoglobin value).

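### Hypercalcemia is named as the harm of very high-dose vitamin D, but no scheduled test measures serum calcium

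*Combined protocol and SAP*

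**What the plan says.** **The harm.** Section 5.4.2.2 says that vitamin D in very high doses "can cause high levels of calcium in the blood (hypercalcemia"), with renal stones, renal damage and deposits in heart and lungs as possible consequences. It also calls prolonged intake above 4,000 units daily possibly unsafe for this reason. It then accepts that "much higher doses are often needed for the short-term treatment of vitamin D deficiency". Section 5.4.8 repeats the hypercalcemia risk.

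**The safeguard.** Section 5.4.2.2: "We will monitor blood levels of vitamin D to minimize the risk of these side-effects". Section 5.4.8 names no analyte: "We will monitor blood levels to minimize these risks". Under 5.4.2.1 the 25OH vitamin D level is repeated one week after the last 50,000 IU dose, then every four months, and dosing is adjusted to keep it above 40 ng/ml.

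**The laboratory tests.** Section 6.5 lists the chemistries as "sodium, potassium, chloride, CO₂, glucose, BUN, creatinine" and the second panel as "Liver function tests (ALT, AST, alkaline phosphatase, total protein, albumin, total and direct bilirubin"). The Schedule of Events has a general chemistry row at visits 0, 2, 3 and 4 and a vitamin D row at seven of the eight visits. Neither it nor Appendix B has a calcium entry.

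**Recording.** Section 7.1.7: "Laboratory abnormalities that are defined as clinically significant are to be considered AEs and recorded on the AE CRF page". Section 7.1.10 captures "Any laboratory test result that is clinically significant or meets the definition of an SAE". Under 8.1, findings that the investigator judges not clinically significant need not be listed as adverse events.

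**The concern.** The protocol identifies a specific biochemical harm of one of its two agents and then measures exposure to the agent, not the harm. The 25OH vitamin D target has a floor and no ceiling. Section 5.4.2.2 is headed as covering modification and discontinuation, but it gives no level at which either happens. The individual discontinuation criteria in 5.4.6 contain no calcium or 25OH vitamin D criterion. Omega-3 is treated differently: a low AA/EPA ratio halves the dose (5.4.1.2), and clotting time is scheduled because of the bleeding concern (5.4.1.3).

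This is a matter of participant safety and of the completeness of the adverse event data. The rules in 7.1.7, 7.1.10 and 8.1 cannot act on an analyte that is not measured. Symptoms are an imperfect substitute: nausea, vomiting and constipation are listed both for excess vitamin D and for omega-3, so in Arm A a calcium value would help to tell the causes apart. Section 5.4.2.3 keeps out hyperparathyroidism and sarcoidosis because they can raise calcium, yet screening has no calcium test that might reveal an undiagnosed case.

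**Working it through.** The plan gives no figure of its own to reproduce. The check has four parts.

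**1. Is calcium scheduled anywhere?** Section 6.5 lists seven chemistry analytes, none of them calcium, and a liver panel that includes albumin but not calcium. The Schedule of Events and every Appendix B table (adults and each child weight band) have no calcium row or volume. Scheduled calcium measurements: 0, in either arm.

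**2. Exposure during loading.** Inputs: 50,000 IU weekly below 30 ng/ml (5.4.2.1), and the upper intake levels tabulated there (3,000 IU for ages 4-8, which covers enrolled children aged 6-8; 4,000 IU from age 9).
- Daily average: 50,000 / 7 = 7,143 IU.
- Against 4,000 IU: 7,143 / 4,000 = 1.79.
- Against 3,000 IU: 7,143 / 3,000 = 2.38.

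Loading lasts 2 months at 20-29 ng/ml. Below 20 ng/ml it lasts 4 months in 5.4.2.1 and 6 months in the synopsis. Listed maintenance doses are 500-2,000 IU/day, below both limits. They are not a ceiling, because 5.4.2.1 lets participants already on replacement keep other doses.

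**3. Would routine visit chemistry be timed to see a rise during loading?** Assume that loading starts at baseline and a month is 30 days (the Schedule puts month 4 at day 120). The visit 2 window is 120 ± 14 = days 106-134.
- Single 2-month course: ends about day 60. Gap to visit 2: 106 - 60 = 46 to 134 - 60 = 74 days.
- Repeated 2-month course (5.4.2.1 repeats loading in children not above 30 ng/ml): redraw about day 67, second course to about 67 + 60 = day 127, inside the visit 2 window.
- 4-month course: ends about day 120, at visit 2.
- 6-month course: ends about day 180, so visit 2 falls within it.

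Only the single 2-month course would finish well before any chemistry draw. For that course the existing post-loading redraw matters most.

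**4. Blood volume, lightest band (16 to < 17 kg).** Limits at 16 kg: 16 × 9.5 = 152 mL per 8 weeks and 16 × 5 = 80 mL per day.
- Redraw: 3.5 mL for 25OH vitamin D plus, if a separate tube is needed, 3.5 mL for calcium and albumin = 7 mL.
- Redraw plus visit 2 within 8 weeks: 39.3 + 7 = 46.3 mL, well under 152 mL.
- Visit 4 already takes 77.8 mL. A further 3.5 mL tube there would give 77.8 + 3.5 = 81.3 mL, just over 80 mL. At the scheduled visits the assays should therefore go on the chemistry sample already drawn.

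**The case against.** The strongest reply is that loading is just the case that 5.4.2.2 allows: time-limited treatment of low levels, for which doses above the general limit are accepted. It starts only below 30 ng/ml, and the 25OH vitamin D level is checked a week after it ends. Conditions that predispose to high calcium are kept out (5.4.2.3). BUN and creatinine are drawn at visits 0, 2, 3 and 4 and bear on kidney damage, one of the named consequences. Adverse events are reviewed by the DSMB about every three to six months (7.1.6), and the investigator may stop treatment at any time.

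Much of this stands, and it limits the point. A reader might infer from the 1.8 and 2.4 ratios that participants are being overdosed or that hypercalcemia is likely. The documents do not support that: they give no hypercalcemia risk and no count of participants who will be loaded. A reader might also infer that all hypercalcemia would be missed. That too goes beyond the text, since symptomatic cases can be reported, and mild rises judged not clinically significant would not be adverse events even if measured. A laboratory might report calcium with its usual panel, but the plan does not ask for it and its itemized list leaves it out.

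What the reply does not supply is a calcium measurement. Creatinine would move only after kidney effects had begun, and 25OH vitamin D without an upper action level triggers nothing when it is high.

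**Conclusion.** The point holds as a participant-safety gap that should be closed. Followed exactly, the plan includes no test that would find a clinically significant but asymptomatic rise in calcium, although it names hypercalcemia as the harm of very high-dose vitamin D. Both arms follow the same vitamin D rules, so the gap covers all 56 planned participants. It matters most for those who start below 30 ng/ml, particularly children aged 6-8.

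Its size can be stated only as exposure: an average of 7,143 IU/day during loading, against tabulated limits of 4,000 and 3,000 IU. The timing figures assume loading from baseline and 30-day months. A reader might infer that the treatment comparison is biased. Nothing in the documents supports that: vitamin D dosing and monitoring are common to both arms, and the primary efficacy comparison is unaffected.

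**What to change.** - **Section 6.5:** add serum calcium to the chemistry panel, run on the chemistry sample already drawn at visits 0, 2, 3 and 4. Appendix B already runs the pregnancy test from that sample. Use albumin, which 6.5 lists, for correction. Confirm that albumin is run at those visits and can share the sample, because liver tests have no row of their own in the Schedule of Events or Appendix B.
- **Post-loading redraw:** for participants given 50,000 IU weekly, add calcium and albumin to the 25OH vitamin D redraw one week after the last dose. Enter that redraw in the Schedule and Appendix B, where it is now missing.
- **Section 5.4.2.2:** state the calcium and 25OH vitamin D levels at which the dose is reduced or held. The values are for the investigators to set. Abnormal results can be handled under 7.1.10 and 8.1 as they stand.

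The cost is a calcium assay at four visits (plus albumin if it is not already run there), two assays and at most one further 3.5 mL tube at the redraw, and follow-up of incidental mild elevations. Sample size and the primary analysis do not change.

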6.6. Mechanistic Outcome Assessments

The DRI will perform immune assays to further understand mechanisms that may be underlying the Type 1 disease process and response to therapy. For this purpose, samples will be obtained and stored for future analysis.

Mechanistic Assessments: includes samples for RNA, plasma, serum, DNA, measures of B and T cell number/function and cytokine profiles

6.7. Metabolic Outcome Assessments

Metabolic assessments will consist of:

- Glucose records and reports of hypoglycemia
- Insulin dose
- HbA1c
- Clarke Score

- Mixed meal tolerance test (MMTT)

6.8. Visit Windows

The initial study drug administration must begin within 180 days from the day of diagnosis. All subsequent treatment visits and follow up visits in Appendix 1 must occur within the time limits specified below:

The table below depicts summary of visit windows.

Visit Windows	
Visit 0	At least 2 weeks before visit 1
Visit 1	New onset group (randomization \leq 180 days from T1D diagnosis) or established T1D ($>$ 180 days and $<$ 10 years from T1D diagnosis)
Visit 2-4 (Days 120, 240, 360)	\pm 14 days
Follow-up between year 1 and 2	
Every four months	\pm 14 days

During the course of the study, participants who complete one year treatment will receive combination therapy of Omega-3 Fatty Acids and Vitamin D or Vitamin D alone. In addition, participants will frequently undergo assessments of their insulin production, immunological status, and overall health. The participant's insulin production will be measured by a series of MMTTs conducted regularly during the study. The participant's diabetes control will be evaluated by measuring HbA1c every four months and clinical records including insulin types, doses, administration times and blood glucose records.

6.9. Unscheduled visits

Patients will be instructed to contact the study coordinator for any health concern, side effects potentially associated with the study, or other concern that may affect their participation and require an unscheduled visit.

6.10. Sample retention

Specimens for future mechanistic studies will be obtained throughout the study. Residual specimens may be used by the investigators for studies of immunologic mechanisms involved in T1D. Specimens collected in this trial may be used to reevaluate biologic responses as new research tools become available. These specimens will be encoded with specific study ID and stored at the Diabetes Research Institute of University of Miami.

6.11. Staggering Administration

Please note that the enrollment of patients in this trial is staggered across individuals. Initially, a total of 6 subjects will be randomized in each of the following groups:

Group	Subject population
I	Fourteen (14) adults (18-65 years) of established T1D of more than 6 months duration (>180 days) and up to 10 years
II	Fourteen (14) adults (18-65 years) of new-onset T1D diagnosed within last 6 months (\leq 180 days)
III	Fourteen (14) children (6-17 years) of established T1D of more than 6 months duration (>180 days) and up to 10 years
IV	Fourteen (14) children (6-17 years) of new-onset T1D diagnosed within last 6 months (\leq 180 days)

All 24 subjects will be monitored for acute and subacute adverse events for 90 days and a formal DSMB (Data and Safety Monitoring Board) will review the data and safety prior to treating additional subjects. This will limit the number of subjects who might be exposed to any unanticipated safety risk.

6.12. Intensive T1D Management

During the study period, all participants will receive “intensive” management of their diabetes. The goal of the treatment will be to keep the HbA1c levels within the currently recommended American Diabetes Association age-specific target range in the absence of significant or level 3 hypoglycemia or diabetic ketoacidosis. The primary responsibility for diabetes management will be the treating or referring diabetes care provider, but the research study team will provide close additional support through regular interaction at study visits. Subjects will not be permitted to use non-insulin pharmaceuticals for glycemic control. Glucose levels should be checked frequently and records of the glucose levels communicated to the study team at study visits.

6.13. Safety Monitoring

The members of the Data Safety Monitoring Board (DSMB) are independent and serve in an individual capacity to provide their expertise and recommendations. They will review the 90 day data of the first 6 subjects, and then periodically review and evaluate the accumulated study data for participant safety, study conduct and progress, and, when appropriate, efficacy, and make recommendations to study investigators concerning the continuation, modification, or termination of the trial. The DSMB members will comprise of experts in the field of T1D immunotherapy and will consider study-specific data as well as relevant background knowledge about the disease, test agents, and patient population under study.

The DSMB is responsible for defining its own deliberative processes, including event triggers that would call for an unscheduled review, stopping guidelines, and voting procedures prior to initiating any data review.

6.14. *Ad-hoc* DSMB Reviews

In addition to the pre-scheduled data reviews and planned safety monitoring, the DSMB may be called upon for ad hoc reviews. The DSMB will review any event that potentially impacts safety at the request of the study investigator. In addition, the following events will trigger an *ad-hoc* comprehensive DSMB Safety Review:

- Any death that occurs in the study.
- The occurrence of a Grade 3 or higher related and unexpected SAE in three or more of the study participants who have received a study treatment.

After review of the data, the DSMB will make recommendations regarding study conduct and/or continuation.

